Vestibular Rehabilitation (VR) is a program consisting of exercises designed to address the impairments, functional limitations, and disability from vestibular hypofunction. Walking for endurance is cited as one of the components of vestibular rehabilitation in the “Clinical Practice Guideline for Peripheral Vestibular Hypofunction” together with gaze stability, habituation, and

balance training.²⁵ Aside from the general conditioning value of walking as an exercise, walking develops or maintains the efficiency of the two vestibular reflexes, consisting of the vestibulospinal and vestibuloocular reflexes involved in postural control.¹² Walking involves sensory integration of inputs from visual, vestibular and somatosensory for controlled translation of the center of gravity. In addition, walking is a form of physical activity accessible to all persons regardless of socioeconomic status. Although walking can offset the avoidance of physical activity from symptom provocation, no direct evidence has been found to support the effect of walking on postural and dynamic stability, function, and participation in people with dizziness.²⁵

To evaluate the effectiveness of vestibular rehabilitation, various outcome measures have been utilized in the literature. Guided by the International Classification of Functioning, Disability and Health (ICF) as the biopsychosocial model, The Academy for Neurologic Physical Therapy created The Vestibular Evidence Database to Guide Effectiveness (VEDGE) task force that evaluated the domains targeted in vestibular rehabilitation namely: body structures and functions (postural stability, dynamic stability, gaze stability, VOR function), activity and participation restrictions and symptom severity. Among the outcome measures recommended by the task force are the Dynamic Gait Index (DGI), Timed Up and Go (TUG) tests, and Modified Clinical Test of Sensory Integration of Balance (mCTSIB) for postural or dynamic stability, and the Dizziness Handicap Inventory (DHI) for activity or participation for the general vestibular population.²⁶

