There are four purposes to this study. The primary purpose of this study is to evaluate the impact of walking as an exercise component of VR on both primary and secondary vestibular-specific outcome measures. The primary outcomes are mCTSIB, TUG test, DGI, and DHI, while the secondary outcomes are the total number of visits and length of interventions (in weeks). The second purpose is to evaluate whether pedometers increase the adherence of older adults with vestibular issues to a walking program. This will be measured by change in physical activity, as represented by International Physical Activity Questionnaire (IPAQ) Walking Metabolic Equivalent of Task (MET)-minutes/week and IPAQ Total Physical Activity MET-minutes/week scores from the IPAQ short form during the episode of care (admission and discharge) and on four-weeks follow-up compared to those patients who only received instructions to walk without a pedometer. The third purpose of this study is to establish test-retest reliability of the TUG test on older adults with dizziness. Lastly, the fourth purpose of this study to investigate if the TUG, DGI, and mCTSIB are significant and strong predictors of the DHI in older adults with dizziness. Protocol #1365169 “Predictors of Disability in the Older Adults” is being performed to supplement the number of subjects for the fourth objective of this study.

Study Design

Research Design

1. Experimental Design. To answer the first and second study objectives, a pragmatic, randomized, prospective, clinical study on 54 older adults with dizziness will be utilized. This will be conducted at Florida Hospital Sports Medicine and Rehabilitation locations that offer vestibular therapy. These are in East Orlando and Winter Park.
2. Correlation Design. A correlation analysis will be performed on the data collected on 54 subjects in the experimental design to establish the test-retest reliability of the Timed Up and Go.
3. Cross-sectional Descriptive Design. A regression analysis will be performed on three predictors of the Dizziness Handicap Inventory, obtained from the data collected on 54 subjects in the experimental design and from Florida Hospital Sports Medicine and Rehabilitation Physical Therapy medical charts from June 2015 to June 2018 that met the inclusion and exclusion criteria that were outlined in the Protocol #1365169.

Study Agent, Device, and/or Intervention Description

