The TUG is a test of balance and risk for falls.²⁷ This test measures the time it takes to walk 3 meters starting from a sitting position and it ends when the patient is seated again. Among the population studied for the TUG are the frail elderly and vestibular disorders.⁴² The cut-off scores that indicate risk for falls are greater than 13.5 seconds for community dwelling older adults²⁷ and greater than 11.1 seconds for vestibular disorders.²⁹ It has an excellent inter-rater reliability for elderly adults.⁴³ Podsiadlo and Richardson found that in the elderly adults, the TUG has excellent correlation with Berg Balance ($r=-0.81$), gait speed ($r=-0.61$), and Barthel Index of ADL ($r=-0.78$).⁴² It has 80% sensitivity and 56% specificity in falls prediction for vestibulopathic elderly.²⁹ MDCs have been established for Alzheimer's Disease (4.09 seconds)⁴⁴ and

Parkinson's Disease (3.5 to 11 seconds).⁴⁵⁻⁴⁷ There is no established MDC for older adults with dizziness.

The DGI assesses the ability to maintain balance while walking in the presence of external demands. It is scored based on a 4-point ordinal scale (3=no gait dysfunction, 2=minimal impairment, 1=moderate impairment and 0=severe impairment) with the highest possible score of 24.³³ A cut-off score of less than 19 is indicative of increased fall risks in community-dwelling elderlys.⁴⁸ It has an excellent intrarater (ICC=0.89) and interrater (ICC=0.82) reliability for community dwelling older adults with baseline impairment⁴⁹ and adequate inter-rater reliability ($k=0.64$) for the vestibular population.³³ It has excellent correlation with Balance Self-Perceptions test ($r=0.76$) and Berg Balance Test ($r=0.67$) and adequate correlation with assistive devices history ($r=-0.44$) and history of imbalance ($r=-0.46$) in community dwelling older adults;⁴⁸ and excellent concurrent validity with the Berg Balance Scale ($r=0.71$) in the vestibular population.⁵⁰

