The principal investigator may share the research data with accreditation organizations and regulatory agencies, dissertation committee, and publications, medical meetings, or scientific journals for the purposes of completing the research study, and analyzing and evaluating the results. Individual patients (subjects) will not be identified during data sharing, and a research number will be used instead during the data sharing process, unless necessary to carry out the research study or required by law.

Sample Size Determination

A priori power analysis predicting a large effect size ($F=.25$) determined that a total of 54 subjects (18 in each group), who met the inclusion and exclusion criteria will be needed, with alpha at the conventional value of .05 to achieve a .80 power, that includes an assumption of a dropout rate of 10% .

Statistical Analysis Plan

The results will be presented through the following tables with supporting explanations:

- Clinical and sociodemographic characteristics of participants by group at baseline.
- Comparisons of TUG, DGI, mCTSIB and DHI between the three intervention groups on admission and discharge.
- Comparisons of self-reported walking activity (walking MET-min/week) and total self-reported energy expenditure (total physical activity MET-min/week) as determined from the IPAQ short form on admission, discharge and four-week follow-up between the three intervention groups
- Comparisons of averages of compliance to step log recording and compliance rate for meeting step goal between the VRWP and VRW groups. Compliance is defined as low (<33%), moderate (33%-75%) and high (>75%) based on the step log or walking log. This grading of compliance was used by Hall and colleagues in their research on efficacy of gaze stability exercises in older adults with dizziness.⁵³
- Comparisons of total number of visits and length of interventions in weeks between the three intervention group.
- Intraclass Correlation Coefficients for the Timed Up and Go test-retest reliability
- Result of stepwise linear regression analysis for TUG, DGI, mCTSIB and DHI

All interval and ratio data will be tested for normality prior to undertaking the data analysis. Descriptive statistics will be used to describe the characteristics of the sample and compare the three groups at baseline. This will include Analysis of Variance (ANOVA) for parametric and Chi Square for nonparametric sociodemographic and clinical data.

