Analyses will employ five repeated measures Analysis of Covariance (ANCOVA), adjusting for age, with two independent variables (group and time) and five outcome measures (TUG, DGI, DHI, mCTSIB and IPAQ short form). The adjustment of age is based on age-related decline. Intraclass Correlation Coefficient will be calculated to establish the test-retest reliability of the TUG and a stepwise linear regression with age as covariate will be conducted for all 54 subjects at baseline to determine if TUG, mCTSIB and DGI are predictors of DHI. Two-tailed test will be utilized to compare the compliance with step log recording and meeting step goals between the two walking groups (VRWP and VRW), and ANOVA to compare of total number of visits and total length of intervention in weeks between the three groups. Alpha for all analyses will be set at 0.05 to test for significant difference.

Potential Risks and Benefits

Potential Benefits

Possible benefits include improved physical function.

Potential Risks

The addition of a prescribed walking program in the treatment of dizziness will challenge the subject's balance, and in rare cases may result in falls or more dizziness.

Performance-based outcomes such as mCTSIB, DGI, and TUG check for the subject's reaction whenever in a condition of unsteadiness. The risks associated with these tests are the potential for falls and for dizziness. Self-report questionnaires such as the DHI and IPAQ will need the subject to read the questions and recall past experiences. Looking down and reading the questions may provoke dizziness and eye strain. Other possible risks for subjects are: 1) finding the questions to be sensitive 2) emotional discomfort (uncomfortable/embarrassed/sad/tired) and 3) distress as subject thinks of experiences.

Mitigation of Risks

The research staff (treating physical therapist) will supervise the treatment at all times to minimize any such risks.

Provisions to Protect the Privacy Interest of Subjects

Subjects will be assigned research numbers for study-related records and data sharing. The patient's confidentiality will be protected by observing the HIPAA policies and procedures.

Early Withdrawal of Subjects

Investigator Withdrawal of Subjects

The PI may terminate the participation of the subject in the study if the subject may be in any danger or no longer meets the inclusion criteria of the study.

Subject Request for Withdrawal from Study

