The Bland-Altman plots show the distribution of the difference scores of two measurements around zero. The 95% level of agreement means that 95% of the difference scores fall within two standard deviations above or below the mean of the difference scores. Values closer to zero means greater reproducibility between two repeated measures.

Objective 4. To investigate if the TUG, DGI, and mCTSIB are significant and strong predictors of the DHI in older adults with dizziness.

The subjects were then grouped based on the DHI test results, using the categories suggested by Whitney et al: 0-30 for mild, 31-60 for moderate, and 61-100 for severe.¹⁰⁴ This analysis is similar to the work of Vereeck et al⁸⁴ to obtain a better picture between the dependent variable DHI and the independent variables: mCTSIB, TUG, and DGI. Kruskal-Wallis analysis was calculated to compare group means for age, mCTSIB, TUG, and DGI. The significance values were adjusted by the Bonferroni correction for multiple tests.

Before the multiple linear regression analysis, assumptions were tested to establish the nature of the data. The obtained Durbin-Watson statistic for the analysis of the independence of

observations is 2.639. The Durbin-Watson statistic can range from 0 to 4, with a value of approximately 2 to indicate that there is no correlation between residuals. The obtained value is close to 2, therefore it can be accepted that there is the independence of observations. The assumptions of homoscedasticity, normality, and multicollinearity are upheld. There is no presence of outliers in the data.

The Spearman Rho correlation coefficients were calculated to establish the relationships between the DHI and mCTSIB, TUG and DGI. As a general guideline, the value 0.00 to .25 indicates little to no relationship, 0.25 to 0.50 suggests fair relationship, 0.50 to 0.75 denotes moderate to good relationship and above .75 is considered good to excellent relationship.⁴⁴ Then, a multiple linear regression analysis was conducted for a continuous dependent variable and three independent variables to identify the predictors of DHI.

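### The protocol and SAP do not agree on which subjects, which selection method and which age adjustment the Objective 4 regression of the DHI uses

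*Combined protocol and SAP*

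**What the plan says.** Four places describe the same regression.

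- **Study Objectives.** A companion chart protocol "is being performed to supplement the number of subjects for the fourth objective of this study".
- **Research Design, Cross-sectional Descriptive Design.** The three predictors of the DHI are "obtained from the data collected on 54 subjects in the experimental design and from Florida Hospital Sports Medicine and Rehabilitation Physical Therapy medical charts", for June 2015 to June 2018. The number of charts is not given.
- **Statistical Analysis Plan.** The list of results tables includes "Result of stepwise linear regression analysis for TUG, DGI, mCTSIB and DHI". The analysis text then says that "a stepwise linear regression with age as covariate will be conducted for all 54 subjects at baseline". No entry or removal limits are given.
- **Data Analysis, Objective 4** (past tense). "a multiple linear regression analysis was conducted for a continuous dependent variable and three independent variables to identify the predictors of DHI". No N, data source, entry method or age adjustment is stated. Age appears there only as a variable compared across DHI severity groups. The section adds: "The assumptions of homoscedasticity, normality, and multicollinearity are upheld". It gives no variance inflation factors and no correlations among the predictors.

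**The concern.** The first problem is the sample. The trial participants alone and the trial participants plus charts are different analysis sets, and both descriptions are current text. An analyst who follows the Statistical Analysis Plan would discard the data gathered to strengthen this objective.

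The second is the method. Objective 4 asks about each of three named measures. The background section places all three in one domain: "Dynamic Gait Index (DGI), Timed Up and Go (TUG) tests, and Modified Clinical Test of Sensory Integration of Balance (mCTSIB) for postural or dynamic stability". If they overlap, stepwise entry can keep one and drop another that is also related to the DHI, which would then be read as not a predictor. The p-values and R-squared of the selected model take no account of the selection.

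The third is age. It is planned as a covariate and then not mentioned in the regression that was described. At stake is the interpretation of one of the four stated purposes, for which a separate paper is planned.

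**Working it through.** **1. The descriptions side by side**

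| Section | Sample | Selection | Age |
|---|---|---|---|
| Study Objectives / Research Design | 54 trial + charts | not stated | not stated |
| Statistical Analysis Plan | 54 trial | stepwise | covariate |
| Data Analysis, Objective 4 | not stated | none stated | not stated |

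The first two rows conflict on the sample. The third does not settle it.

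**2. Where 54 comes from**

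Sample Size Determination gives effect size .25, alpha .05, power .80 and 10% dropout, without naming the test. One setting reproduces the figure: the group-by-time test with three groups, three time points and an assumed correlation of .3 needs 48, and 48/0.9 = 53.3, rounded up to 54. With two time points and correlation .5 the need is 42, and 42/0.9 = 46.7, or 47. In each case 54 is a size for the three-group comparison. No sample size is given for the regression.

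**3. What the sample choice does to power**

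The test is of one predictor, two-sided alpha .05, with three predictors and age in the model: noncentral F with 1 and N−5 degrees of freedom and noncentrality f² × N. For f²=.10 and N=54 these are 1 and 49 degrees of freedom and noncentrality 5.4. The partial f² and every N other than 54 are assumptions.

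| Partial f² | N=54 | N=100 | N=150 | N=200 |
|---|---|---|---|---|
| .10 | 62% | 88% | 97% | 99% |
| .05 | 36% | 60% | 78% | 88% |

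At N=54, 80% power needs f² of about .152, a partial r of √(.152/1.152) = .36.

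**4. How stable stepwise selection would be at N=54**

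Simulation with assumed entry p<.05 and removal p>.10, 1,500 samples per setting, age left out. Forcing in an age term unrelated to the other variables did not change the first case.

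- *Three equally related predictors* (r with the DHI .3 or .4, inter-correlation .5 or .7): exactly one is kept in 72% to 93% of samples, all three in 0.4% or fewer, and any given one in about 26% to 43%.
- *One stronger predictor* (r .5 against .3 and .3; same inter-correlations): the stronger one is kept in about 91% (inter-correlation .5) and 96% (.7).

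A separate simulation with age forced in used one true predictor (slope .4). A wrong predictor was kept without the true one in about 4%, 9% and 17% of runs at inter-correlation .3, .5 and .7.

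**5. Selection also depends on N**

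With three equal slopes of .25 and age forced in, the share of runs keeping a single predictor is .226+.216+.206 = 65% at N=54 and .015+.015+.013 = 4% at an assumed N=150 (inter-correlation .5). At inter-correlation .7 it is 86% and 16%. Under stepwise selection the two candidate samples could therefore give different answers.

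**6. What the documents imply about overlap**

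Study Outcome Measures gives correlations with the Berg scale of −.81 for TUG and .71 for DGI. If both held in one population, the TUG–DGI correlation would lie within (−.81)(.71) ± √[(1−.81²)(1−.71²)] = −.575 ± .413, that is −.99 to −.16. Overlap is plausible, but its degree is not fixed.

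**The case against.** The strongest reply is that the Data Analysis section overtakes the stepwise plan. Its plain reading is a single model with all three measures, close to what is recommended here. That stands. A reader might infer that the reported predictor of disability was picked by chance. The documents do not support this: no stepwise model is shown to have been run or reported, no inter-predictor correlations are given, and the chance-like result in step 4 follows from assuming equal predictors. It largely disappears when one predictor is clearly stronger.

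A second reply is that entering all three together does not show more of them to be significant. That also stands. In the equal-predictor settings, forced entry makes all three individually significant in only 0.1% to 0.3% of samples and none in 34% to 74%; stepwise selects none in 2% to 22%. With no true predictor, false positives are similar: 11% to 14% for stepwise, 13% to 14% for unadjusted tests in the full model. The case for forced entry is that its intervals and joint test are not distorted by selection; the joint test stays near 5% under the null (simulated 4.7% to 5.5%).

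A third is that this is a cross-sectional secondary purpose that touches neither the randomised comparison nor safety. That is true and limits the weight of the point. It does not remove the conflict over the sample.

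**Conclusion.** The point holds as a conflict over sample, selection method and age adjustment. The sample conflict rests on the text alone and needs no assumption. Its size cannot be fixed because the chart N is not given; if the total were 100 rather than 54, power for one predictor with partial f²=.10 would be 88% rather than 62%.

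The criticism of stepwise selection applies to the plan as written. The size of the instability rests on assumed correlations and entry limits and runs from serious (equal predictors) to slight (one clearly stronger). It should not be read as a finding about the model finally reported. The statement that the multicollinearity assumption was met does not exclude moderate overlap, but neither does it establish any.

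**What to change.** - **Statistical Analysis Plan:** delete the stepwise wording in both the table list and the analysis text, and delete the restriction to the 54 trial participants. Specify one linear model for the DHI on the trial-plus-charts set of the Research Design section, with TUG, DGI, mCTSIB, age and a data-source indicator entered together.
- **Reporting:** give each coefficient with its 95% confidence interval, the joint test of the three balance measures, and R-squared. Show the same model on the 54 trial participants, without the source indicator, as a sensitivity analysis.
- **Data Analysis, Objective 4:** state N by source, the entry method and whether age was adjusted for, so that it matches the plan.

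The cost is revised wording and one re-run regression. With overlapping measures the individual intervals may be wide, so the joint test should be read alongside them.

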1. Age 65 years or older referred for physical therapy evaluation for symptoms of dizziness, postural instability, or both
2. Able to walk without the physical help of another person, with or with no assistive device
3. Able to follow commands and execute the examination and intervention instructions in the English language
4. Willing to participate in a phone interview four weeks after discharge
5. Able to provide informed consent

Exclusion Criteria

1. Unstable medical issues, such as unstable or uncontrolled cardiovascular conditions, elevated blood pressure (Systolic greater than or equal to 140mmHg and diastolic greater than or equal to 90mmHg), orthostatic hypotension (a fall in systolic blood pressure of at least 20mmHg or diastolic blood pressure of at least 10mmHg when a person stands from a sitting or lying down position), uncontrolled metabolic disease, as determined by the evaluating physical therapist, documented in the Functional Comorbidity Index, vital signs and assessment portion of the initial evaluation.
2. History of falls from syncopal origin
3. Dizziness of central origin, such as stroke, head injuries, MS or PD;
4. Active BPPV (patients with positive dix hallpike and/or roll test)
5. Inability to walk without physical assistance.

Resources Available

Each site will have research staff (treating physical therapists). Prior to enrollment of subjects, training of the study coordinator and research staff will be conducted onsite or online by the principal investigator. This training will cover the following: multi-site communication, subject recruitment, informed consent, inclusion and exclusion criteria and data collection. Research staff will receive instructions on randomization, interventions, outcome measures, and the use of Fitbit Zip pedometer. To establish interrater reliability, participating therapists will rate the DGI, mCTSIB and TUG by watching a video of a volunteer patient, and the DHI and IPAQ short form sample

questionnaires. To ensure compliance with the outcome measure equipment, research staff will sign a Research Equipment Compliance Document. The principal investigator will conduct inspection of equipment in each site, co-sign the document and keep the paper record in a locked filing cabinet in Florida Hospital.

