Visit 2: The research staff can initiate the research intervention according to the intervention group.

Visit 3 to visit prior to discharge: The research staff can continue the VR and intervention according to the intervention group.

Discharge or last visit: All outcome measures (DGI, TUG, mCTSIB, DHI and IPAQ) will be reassessed. Discharge scores for DGI, TUG, mCTSIB and DHI are standard of care, while IPAQ is for research purposes only. The total number of visits and length of

interventions (in weeks) for every participant will be recorded as secondary outcome measures. These research data will be forwarded to the study coordinator, and will be stored in a locked cabinet and password protected Florida Hospital computer.

Four-weeks after discharge: The study coordinator will conduct a follow up phone call to all subjects four weeks after discharge summary is completed to obtain the level of physical activity using the IPAQ short form questionnaire. This is for research purposes only. A follow-up on a subject will be discontinued if a subject is not reached after three attempts of follow-up phone call made on three different days between 30 and 45 days. Data analysis will commence once all the data from 54 subjects are collected.

Table 1. Summary of Interventions for VRWP, VRW and VR Groups.

VRWP (n=18)	VRW (n=18)	VR (n=18)

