Subjects may withdraw or take away the permission to use and disclose their health information for any reasons at any time. This can be done by sending a written notice to the PI. Information that has already been gathered may still be used or given to others, however no new health information that might identify the subject will be gathered after the subject withdraw from the study.

Data Collection and Follow-up for Withdrawn Subjects

Patients who request withdrawal or who are withdrawn by the PI from the study will have their information that has already been gathered and shared in the research database. These data will be included in the data analysis. The percentage of patients withdrawing will be calculated.

Adverse Event Reporting

At each therapy visit of the subject, the research staff/treating therapist will seek information if there is any adverse event caused by taking part in the study. In the event of a research-related injury, the subject should report this in person or by phone to the research staff/treating therapist and PI. All adverse events will be reported to Florida Hospital's IRB and Nova Southeastern University's IRB following their respective policies for reporting adverse events.

Safety Monitoring Plan

Safety Monitoring
N/A

Data and Safety Monitoring Board (DSMB) or Equivalent
N/A

Ethical Considerations

Subjects in the VRW and VR group will receive a pedometer after they completed the study.

Sharing of Results with Subjects

Results of the study that are part of standard physical therapy will be shared with subjects and referring physicians. Letters will be sent to all participants that contain the results of the research once the research is completed.

Funding Source

Application for funding will be done through the Adventist University in January 2018. The principal investigator is currently requesting managers to allow the allocation of her Continuing Education budget for 2018 for this study.

Subject Stipends or Payments

The pedometer will be donated to the 54 participants, who met the inclusion and exclusion criteria and randomized into one of the three treatment groups, as a reward for participating in the research study and for them to perpetuate their physical activity.

Publication Plan

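### Subjects whom the PI withdraws before discharge may have no posttest on the four primary outcomes, and that loss could favour the walking arms

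*Combined protocol and SAP*

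**What the plan says.** Under Investigator Withdrawal of Subjects, the PI has discretion to end a subject's study participation "if the subject may be in any danger or no longer meets the inclusion criteria of the study". The Inclusion Criteria include "Able to walk without the physical help of another person, with or with no assistive device".

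Under Data Collection and Follow-up for Withdrawn Subjects, those "withdrawn by the PI from the study will have their information that has already been gathered and shared in the research database". The section adds that these data are analysed and that the percentage withdrawing is calculated. It describes no collection after a PI withdrawal. The explicit bar on gathering new information stands in a different section, Subject Request for Withdrawal from Study, and concerns subjects who withdraw their permission.

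Under Study Visits, at the discharge or last visit: "Discharge scores for DGI, TUG, mCTSIB and DHI are standard of care, while IPAQ is for research purposes only". Baseline scores are already extracted from the chart by the study coordinator.

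Under Potential Risks, adding the prescribed walking programme "in rare cases may result in falls or more dizziness".

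In the Data Analysis section, Objective 1 compares pretest-posttest differences in the four primary outcomes between the combined walking groups and the control group.

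**The concern.** The grounds for withdrawal overlap with the outcomes. Danger from falls or increasing dizziness, and loss of independent walking, are deterioration on much the same ground that TUG, DGI, mCTSIB and DHI measure. If such a subject is terminated and nothing further is collected, the missing posttest is missing because it would have been poor.

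The loss could also depend on the arm. Only VRWP and VRW receive the walking programme to which the protocol attributes the added risk. The decision rests with the PI, who according to Resources Available is also a treating therapist and so knows the arm of the subjects treated.

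At stake is the main comparison. If poor results leave the walking groups more often than the control group, the observed mean change favours walking. The plan states no missing-data method, intention-to-treat rule or sensitivity analysis. No primary outcome is scheduled between the start of walking and discharge, so the outcome data would hold little trace of the deterioration for a model to use.

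**Working it through.** **Tracing one subject through the plan**

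1. Baseline TUG, DGI, mCTSIB and DHI come from the initial evaluation or first follow-up visit. The extra TUG trials at Visit 1 also precede the walking programme, which starts at Visit 2.
2. Suppose a walking-arm subject deteriorates after Visit 2 and the PI uses the discretion to terminate participation.
3. The section on withdrawn subjects retains what has been gathered. For the primary outcomes that is the baseline only.
4. The Objective 1 analysis needs a difference between pretest and posttest. The subject contributes none, even though the plan says that the retained data are analysed.
5. If the subject goes on with ordinary vestibular rehabilitation and has a discharge assessment, the four scores exist in the chart as standard of care. The plan does not say that they are extracted.

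**Illustrative size on the DHI**

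Inputs from the documents: 18 subjects per arm, so 36 walking and 18 control; DHI MCID of 18 points. Assumed, because the documents give no figures: the number k of walking subjects lost, their true change, an 18-point improvement in the rest, and no control losses. Changes are written as points of improvement.

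Bias = (k/36) × (change in those kept − change in those lost)

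- k = 2, lost subjects unchanged: (2/36) × (18 − 0) = 1.0 point (recorded mean 18, full mean 34 × 18/36 = 17).
- k = 4, lost subjects unchanged: (4/36) × (18 − 0) = 2.0 points (recorded 18, full 32 × 18/36 = 16).
- k = 4, lost subjects worsened by 18: (4/36) × (18 + 18) = 4.0 points.

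Control losses of the same kind offset this. Losing 2 of 18 controls is the same fraction as 4 of 36, (2/18) × 18 = 2.0, and the net bias would be nil. The bias comes from the difference between arms.

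**Pessimistic bound by simulation**

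Normal change scores, no true effect, exactly the k worst of 36 walking subjects removed, no controls removed, two-group rank test at 0.05 (20,000 draws for bias, 6,000 for type I error):

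| k removed | Bias (SD) | Type I error |
|---|---|---|
| 0 | 0.00 | 0.045 |
| 1 | 0.06 | 0.056 |
| 2 | 0.11 | 0.070 |
| 4 | 0.20 | 0.110 |

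Real withdrawals would not pick out exactly the worst subjects in one arm, so for a given k these figures lean high.

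**The plan's dropout allowance**

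Sample Size Determination allows 10% dropout: 0.10 × 54 = 5.4 subjects. Four of 36 is 11%, but the plan's 10% is an overall allowance and not a rate of termination for worsening. It protects power; it does not correct selective loss.

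**The case against.** The strongest reply is that the plan is silent here rather than wrong. A reader might infer that it forbids collecting discharge scores after a PI withdrawal. It does not: the explicit bar covers subjects who withdraw permission. The reference to a discharge or last visit even leaves room for scores to be taken when participation ends. That stands against any claim of a stated prohibition. It does not close the gap, because the section devoted to follow-up of withdrawn subjects names PI withdrawal and provides only for existing data.

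Four other readings go too far.

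- *Every subject who worsens loses the posttest.* Termination is discretionary, so this concerns only those whom the PI chooses to withdraw before discharge.
- *The posttest is always in the chart.* It is there only if a discharge assessment is done; a subject who also leaves therapy may have none.
- *Refusing the phone call costs all four primary outcomes.* Willingness to take the call is an inclusion criterion ("Willing to participate in a phone interview four weeks after discharge"), but the call comes after discharge, when those scores are already held. For subjects not reached, Study Visits stops only the follow-up.
- *Walking will look safer.* Adverse events are sought at each therapy visit and reported to both IRBs, so the documents do not show this. The concern is with the efficacy outcomes.

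The size is also open to challenge. The protocol calls falls or more dizziness rare, and 1 to 2 points is small beside an MCID of 18 and an MDC of 17.18. That is fair for individual change. A bias in a difference between group means is not excused by being smaller than an individual threshold, but the illustration should not be read as a forecast.

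**Conclusion.** The concern holds in a limited form. Followed as written, the plan can lose primary posttests in a way related to outcome and possibly to arm, and the likely direction favours walking. The 1 to 2 DHI points rest on assumed losses of 2 to 4 of 36 walking subjects with no DHI change, 18 points of improvement in the others, and no control losses. The documents supply none of these counts; few or balanced withdrawals would make the bias negligible. The loss is partly avoidable, because the four discharge scores are routine care. The point does not depend on whether 54 is the right sample size, and it takes no position on when a subject should be withdrawn.

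**What to change.** Leave the PI's authority and the withdrawal criteria unchanged. In Data Collection and Follow-up for Withdrawn Subjects, state that:

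- for subjects withdrawn by the PI who have not withdrawn permission, the standard-of-care discharge TUG, DGI, mCTSIB and DHI are extracted from the chart where a discharge assessment is done, and analysed in the randomised arm;
- the four-week IPAQ call is attempted unless the subject declines;
- withdrawals are reported by arm and reason, in place of a single overall percentage;
- the bar on new information continues to apply to subjects who withdraw permission.

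The cost is a little extra chart extraction, a few calls, and consent wording that covers both. The resulting estimate includes subjects who stopped the walking programme early, which may make the apparent effect smaller. Discharge IPAQ is research-only and may still be missing.

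The Data Analysis section is written in the past tense. If collection is over, the call can no longer be made on schedule. Discharge scores could still be sought retrospectively where consent allows, since research records are kept for seven years after closure, and withdrawals can still be tabulated by arm and, where recorded, by reason.
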